### **3.0 ANALYSIS SETS**

The statistical analysis for the PIONEER III Trial will be presented on the following analysis populations. Data for all subjects will be assessed to determine if subjects meet the criteria for inclusion in each analysis population prior to unblinding.

#### **3.1 Intention to Treat (ITT) Analysis Population**

The Intention to Treat (ITT) analysis population will include all randomized subjects in the treatment groups to which they are randomized, regardless of the treatment actually received.

The ITT population will be the co-primary analysis population for the primary safety and efficacy endpoint, the primary analysis population for the powered secondary endpoint, and the primary analysis population for all additional secondary safety endpoints and secondary efficacy endpoints.

#### **3.2 Per Protocol (PP) Analysis Population**

The Per Protocol (PP) analysis population is defined as subjects enrolled in the trial, who meet all major eligibility criteria, and in whom an attempt to implant an assigned study stent has been made. For the purposes of defining the PP population, the following eligibility criteria are defined as “major eligibility criteria”:

	FORM	Document No: BIO-TMP-0702 Revision: 00
	TITLE Statistical Analysis Plan	Effective date: 16-Mar-2018 Department: BIO

- 6.2.1.1.5 The patient or legally authorized representative has been informed of the nature of the study, agrees to its provisions, and has been provided written informed consent approved by the appropriate Institutional Review Board (IRB) or Ethics Committee (EC)
- 6.2.1.2.2 Target lesion(s) must be de novo or previously unstented restenotic native coronary artery lesions (no in-stent restenotic lesions permitted)
- 6.2.2.1.5 [Subject does not have] ST-segment elevation myocardial infarction (STEMI) at index presentation or within 7 days prior to randomization

The PP population will be the co-primary analysis population for the primary safety and efficacy endpoint and the secondary analysis population for all secondary endpoints.

### **3.3 Modified Per Protocol (MPP) Analysis Population**

The Modified Per Protocol (PP) analysis population will include all randomized subjects who receive the assigned treatment per randomization and who have no major protocol deviations. The following will be excluded from the MPP population as specified below:

- Subjects with major inclusion or exclusion criteria deviations (as defined in the PP population definition)
- Subjects whose informed consent was not obtained
- Subjects for whom the randomization assignment was not followed (e.g., subject randomized to BuMA DES but treated with DP EES by error)
- Subjects for whom an incorrect stratification was declared for randomization (e.g., incorrect reporting of a subject's diabetes status or clinical presentation in the randomization from prior to randomization)
- An unplanned staged procedure of a target lesion performed with a device other than the previously implanted device(s)

The MPP population will be used in a sensitivity analysis for the primary safety and efficacy endpoint.

### **3.4 As Treated (AT) Analysis Population**

As Treated analysis population will include all randomized subjects as well as all non-randomized subjects treated with a study stent, classified into treatment according to the treatment actually received. The AT population will be the primary analysis population for all adverse event analyses.

	FORM	Document No BIO-TMP-0702 Revision: 00
	TITLE Statistical Analysis Plan	Effective date: 16-Mar-2018 Department: BIO

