## 8.8 Reporting

### 8.8.1 General Adverse Event Reporting Procedures

Investigators are required to keep records on “all relevant observations, including records concerning adverse device effects (whether anticipated or unanticipated)” according to 21 CFR 812.140. Adverse event collection will occur from the point of study enrollment to study closure. All new or worsening (from baseline) clinically significant adverse events will be captured on the AE CRF through the 5-year follow-up visit. It is the responsibility of the Investigator to assess the subject for adverse events and, if it is determined that a clinically significant AE has occurred, to capture the required adverse event information on the AE CRF. Independent monitoring will be conducted (§13.1) to review source documentation and verify the complete and accurate capturing of adverse events.

The general procedure for investigators reporting any adverse event is as follows:

- If an adverse event occurs, complete all sections of the Adverse Event CRF
- Each unique event/diagnosis must be documented separately
- Documented pre-existing conditions are not considered to be reportable AEs unless there is a change in the nature or severity of the condition

- The AE CRF must be reviewed by the investigator

For adverse events not meeting the criteria for an SAE or (potential) UADE, the Sponsor recommends that the Investigator notify the Sponsor within 10 working days of first learning of the AE using the electronic data capture (EDC) CRF. If necessary, the Investigator may be requested to provide de-identified copies of source documentation (e.g., physician/nurse notes or summaries) regarding the event.

The Investigator must also notify the responsible IRB/EC regarding new and significant safety information and any events identified by SINOMED that require expedited FDA or other regulatory authority reporting as serious, unexpected, and related to the investigational device. It is the responsibility of the investigator to ensure site-specific IRB/EC reporting requirement are met.

The sponsor is responsible for reporting SAEs and device deficiencies to regulatory authorities in line with applicable regulatory requirements and for reviewing the risk analysis, determining the need for corrective or preventative action, and informing investigators and regulatory authorities accordingly.

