### 11.4.7 Additional Analyses

The following data will be summarized using descriptive statistics presented by treatment group in the ITT and PP populations:

- Subject enrollment and data compliance by site and visit (data compliance at each visit is the percentage of patients whose data forms have been collected and entered divided by the percentage of patients whose forms should have been collected and entered)
- Frequency (number and percentage of patients) with each type of concomitant medication
- Frequency (number and percentage of patients) with each site-reported Treatment Emergent AE overall and by MedDRA system organ class and preferred term (a treatment emergent AE is an AE that started or worsened during or after the index procedure)
- Frequency (number and percent of patients) with each site-reported Treatment Emergent Serious AE overall and by MedDRA system organ class and preferred term
- Frequency (number and percent of patients) with each site-reported Treatment Emergent AE or SAE, by CEC-adjudicated relationship to the investigational device or procedure
- Protocol deviations (number and percentage of patients with each deviation type)
- Detailed listings on primary and secondary endpoints, site-reported AE, and protocol deviations

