#### 2.2.2.2 Device Success

Device success is defined as attainment of <30% in-stent residual stenosis of the target lesion measured by QCA using the assigned device [evaluated post-procedure]. Lesions treated with multiple stents in which one stent is an assigned device and  $\geq 1$  is not the assigned device are considered as device failures.

This analysis is a lesion-level analysis performed in the ITT subject population. The primary analysis will include all target lesions in which implantation of the assigned device is attempted in the denominator. As a secondary analysis, the device success analysis will include all target lesions in the denominator, whether or not an attempt to implant the assigned device was made.

In addition, lesions without device success will be reported according to the following classification adapted from the 2019 EAPCI/ESC position statement (Chang et al. Defining Device Success for Percutaneous Coronary Intervention Trials: A Position Statement from the European Association of Percutaneous Cardiovascular Interventions of the European Society of Cardiology. *Eurointervention* 2019; Jaa-642 2019, doi 10.4244/EIJ-D-19-00552) [1] in a lesion-level analysis:

	FORM	Document No BIO-TMP-0702 Revision: 00
	TITLE Statistical Analysis Plan	Effective date: 16-Mar-2018 Department: BIO

- 1) PCI was not attempted
- 2) No device implanted (with or without implant attempt)
- 3) Non-assigned device implanted without attempt to use the assigned device
- 4) Unsuccessful device delivery (i.e., implant attempted but no device ultimately implanted)
  - a) Without crossover to non-assigned devices (i.e., attempted implant of assigned device; did not attempt to implant unassigned device)
  - b) Crossover to non-assigned devices, but still unsuccessful (i.e., attempted to implant assigned device; attempted implant of unassigned device)
- 5) Device implanted outside the intended location
- 6) Non-assigned device implanted after a failed attempt to use the assigned device
- 7) Non-assigned device implanted after successful implantation of assigned device(s)
- 8) Residual stenosis above accepted thresholds (NOTE: threshold is  $\geq 30\%$  based on protocol definition of device success)

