## 5.6 Safety Summaries and Analyses

### 5.6.1 Adverse Events

For site reported adverse events, number of subjects with at least one adverse event will be summarized for all subjects in the AT population overall and by event severity, relation to procedure, and relation to device. In addition, number of subjects with SAEs and UADEs will be summarized for all subjects in the AT population. Subject data listings of all adverse events and serious adverse events, with their relationship to study device/procedure, AE onset date, outcome, and duration will be presented in the data listings.

Site reported death, myocardial infarction, revascularization, stent thrombosis and bleeding events will be summarized in the ITT population as in-hospital events, at 30-days, 6 months, and 1, 2, 3, 4, and 5 years. Descriptive statistics for in-hospital events will include count, percentage, and sample size. Subjects with missing data will be excluded from the denominator. Differences in event rates between the two treatment arms will be summarized descriptively with the difference in percentages, the asymptotic 95% confidence interval for the difference of two percentages, and a p-value based on a chi-squared test. If 20% or more of the expected cell frequencies are less than 5 then a Fisher's Exact Test will be used to test for differences in proportions.

Survival analysis techniques, as detailed in Section 4.3, will be used to analyze the site reported events at 30 days, 6 months, and 1, 2, 3, 4, and 5 years. Summary statistics will include Kaplan-Meier estimated event rates and number of events. The log-rank test will be used for comparing treatments. Hazard ratios and the associated two-sided confidence intervals (Wald's CI) will be estimated by Cox proportional hazards model, including treatment as a covariate.

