### 5.6.2 Device Deficiencies, Malfunctions

All device deficiencies, malfunctions, use errors, and any (serious) adverse events associated with device malfunctions/deficiencies/use errors, as documented in the case report form, will be summarized descriptively by frequency (number and percentage of subjects) in the ITT Population for all subjects and by treatment arm.

	FORM	Document No BIO-TMP-0702 Revision: 00
	TITLE Statistical Analysis Plan	Effective date: 16-Mar-2018 Department: BIO

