## 7.0 APPENDICES

### 7.1 List of Tables, Listings, and Figures

Tables:

- 1) Patient Enrollment and Disposition
- 2) Enrollment by Country (ITT)
- 3) Summary of Visit Compliance, Overall and by Site (ITT)
- 4) Summary of Protocol Deviations (ITT)
- 5) Summary of Major Protocol Deviations (ITT)
- 6) Inclusion or Exclusion Criteria Deviations (ITT)
- 7) Summary of Demographics and Baseline Vital Signs (ITT, PP)
- 8) Baseline Risk Factors and Medical history (ITT, PP)
- 9) Summary of Site Reported Procedure Characteristics (ITT, PP)
- 10) Summary of Procedural Medications (ITT, PP)
- 11) Summary of Site Reported Lesion Characteristics (ITT, PP)
- 12) Summary of Device Utilization by Device Size (AT)
- 13) Primary Endpoint Analysis of TLF at 12 Months – CEC Adjudicated (ITT, PP, MPP)
- 14) Sensitivity Analysis of Primary Endpoint at 12 Months (ITT, PP)
- 15) Subgroup Analysis of the Primary Endpoint of TLF at 12 Months (ITT, PP)
- 16) Summary of MI Event Types According to Multiples of the 99th Percentile Upper Reference Limit of Cardiac Biomarkers (ITT)
- 17) Summary of Acute Success Defined by QCA (ITT, PP)
- 18) Summary of CEC Adjudicated In-Hospital Clinical Events (ITT, PP)
- 19) Summary of In-Hospital CEC Adjudicated Revascularization, Bleeding, and Stent Thrombosis Events (ITT, PP)
- 20) Summary of CEC Adjudicated Clinical Events within 30 Days of Randomization (ITT, PP)
- 21) Summary of CEC Adjudicated Revascularization, Bleeding, and Stent Thrombosis Events within 30 Days of Randomization (ITT, PP)
- 22) Summary of CEC Adjudicated Clinical Events within 6 Months of Randomization (ITT, PP)
- 23) Summary of CEC Adjudicated Revascularization, Bleeding, and Stent Thrombosis Events within 6 Months of Randomization (ITT, PP)
- 24) Summary of CEC Adjudicated Clinical Events within 1 Year (2, 3, 4, 5 Years) of Randomization (ITT, PP)
- 25) Summary of CEC Adjudicated Revascularization, Bleeding, and Stent Thrombosis Events within 1 Year (2, 3, 4, 5 Years) of Randomization (ITT, PP)
- 26) Summary of Site Reported In-Hospital Clinical Events (ITT)
- 27) Summary of Site Reported 30 Day Clinical Events (ITT)
- 28) Summary of Site Reported 6 Month Clinical Events (ITT)
- 29) Summary of Site Reported 1 Year (2, 3, 4, 5 Year) Clinical Events (ITT)
- 30) Summary of Adverse Event Characteristics (AT)
- 31) Summary of Device Deficiencies, Malfunctions, Use Errors or Device Misuse (ITT)

	FORM	Document No BIO-TMP-0702 Revision: 00

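### SAP reports general AE, SAE and UADE summaries only As Treated, against Protocol 11.4.7 (ITT and PP), with no rule for failed, mixed or absent stents

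*SAP*

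**What the plan says.** - **SAP 3.4 (As Treated).** The set holds all randomised subjects plus any non-randomised recipient of a trial device, each "classified into treatment according to the treatment actually received. The AT population will be the primary analysis population for all adverse event analyses".
- **SAP 5.6.1, first paragraph.** For site-reported events, the "number of subjects with at least one adverse event will be summarized for all subjects in the AT population", overall and by severity and by relation to procedure and device. SAE and UADE counts use the same set. Table 30, the only general AE summary in the SAP table list, is labelled AT only.
- **Protocol 11.4.7.** Treatment-emergent AEs and SAEs, overall and by MedDRA system organ class and preferred term, are to be "summarized using descriptive statistics presented by treatment group in the ITT and PP populations". The protocol defines no As Treated set.
- **SAP 2.2.2.2.** The reasons for missing device success include no device implanted, unsuccessful delivery, "Non-assigned device implanted after a failed attempt to use the assigned device", and a non-assigned device added after the assigned one.
- **Safety analyses kept by assigned arm.** Secondary safety endpoints are ITT (SAP 5.3.3). The second paragraph of SAP 5.6.1 states: "Site reported death, myocardial infarction, revascularization, stent thrombosis and bleeding events will be summarized in the ITT population". Under SAP 5.6.2, device deficiencies, malfunctions, use errors and their associated AEs "will be summarized descriptively by frequency (number and percentage of subjects) in the ITT Population".

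**The concern.** Three things come together.

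First, the SAP changes the analysis population for the general AE tables and omits the MedDRA breakdown. SAP 1.0 says a significant modification will be reflected in a protocol amendment or the final report. The SAP is based on protocol version 8.0, which still says ITT and PP, and it does not flag the difference.

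Second, the treatment received is not defined for subjects with a failed attempt, mixed stents or no stent. The operator is not among those blinded (Protocol 11.5.2), so a switch of device is an unblinded choice made after randomisation and possibly prompted by the complication itself. Subjects with no stent are in the AT set, because it includes everyone randomised, yet they have no obvious column. Protocol 6.3 follows them to 12 months for safety.

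Third, AT admits subjects who were never randomised. Enrolment is the moment of randomisation (Protocol 6.5), and "Adverse event collection will occur from the point of study enrollment to study closure". Such subjects would enter denominators without a defined start of AE collection.

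At stake is whether the general AE table shows procedural harms, such as the dissection, perforation or distal embolisation listed in Protocol 8.9, in the arm whose device was being tried.

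**Working it through.** **Step 1: which arm would one subject appear in?** Take a subject randomised to BuMA in whom the BuMA attempt fails, an AE follows, and only DP EES is implanted.

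- ITT endpoint tables (SAP 3.1): BuMA.
- Device success (SAP 2.2.2.2): BuMA, because the denominator is lesions with an attempt at the assigned device.
- PP (SAP 3.2): still eligible, because the criterion is an attempt to implant the assigned stent.
- Malfunction table (SAP 5.6.2), if recorded as a deficiency: BuMA.
- General AE table (SAP 5.6.1, Table 30): DP EES, on the natural reading of SAP 3.4.

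Only the last table would move the subject.

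**Step 2: arm sizes.** The plan gives no AE rate or crossover rate by arm, so there is no plan figure for this point to reproduce. The arm sizes do check. The Farrington-Manning calculation (2:1, control rate 6.5%, margin 3.575%, one-sided 0.025; restricted null rates 8.15% and 4.58%) gives 516.2 controls, rounded up to 517, total 1551, with 80.1% power. Then 1551/0.95 = 1632.6, against the stated 1632 (1088:544).

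**Step 3: effect of moving subjects.** Let e be the number with the AE and n the arm size. RD = 100 × (e_BuMA/n_BuMA − e_DP/n_DP). Moving k BuMA subjects, all with the AE, gives

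RD_AT = 100 × [(e_BuMA − k)/(1088 − k) − (e_DP + k)/(544 + k)].

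One moved event shifts RD by roughly 100 × (1/1088 + 1/544) = 0.28 points; two thirds of that falls in the smaller arm.

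Assumed counts are 33 and 11. Both rates lie in the 1% to <10% band in which Protocol 8.9 places coronary dissection.

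| k moved | BuMA | DP EES | RD, points (95% CI) |
|---|---|---|---|
| 0 (assigned) | 33/1088 = 3.03% | 11/544 = 2.02% | +1.01 (−0.55 to 2.57) |
| 5 | 28/1083 = 2.59% | 16/549 = 2.91% | −0.33 (−2.02 to 1.37) |
| 11 | 22/1077 = 2.04% | 22/555 = 3.96% | −1.92 (−3.75 to −0.09) |

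**Step 4: dependence on the assumptions.**

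- *Half of crossovers have the AE; 5% AE rate elsewhere; 1% cross over (10.9 subjects).* Assigned: (53.9 + 5.4)/1088 − 5% = +0.45. As received: 5% − (27.2 + 5.4)/554.9 = −0.88.
- *Real excess outside crossovers (3% vs 2%); 20% of 11 crossovers have the AE.* Assigned: 34.5/1088 − 10.9/544 = +1.17. As received: 32.3/1077 − 13.1/555 = +0.64. The difference is diluted, not reversed.
- *Crossover in both directions at 1%, all with the AE; 5% elsewhere.* Assigned: 0. As received: 5.5% vs 6.9%, RD −1.4.
- *Crossovers have the same AE risk as everyone else.* The shift is about zero.

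**The case against.** The strongest reply is that most safety reporting stays by assigned arm. TLF is analysed in ITT and PP; the secondary safety endpoints and site-reported death, MI, revascularisation, stent thrombosis and bleeding are in ITT. AEs tied to a malfunction, deficiency or use error, where many delivery failures would be recorded, are also in ITT. A reader might infer from the words of SAP 3.4 that all safety comparisons are as treated, or that the trial's safety conclusion could be reversed. The documents do not support either reading: SAP 5.3.3, the second paragraph of 5.6.1 and 5.6.2 say otherwise, and the AE tables are descriptive, with no success criterion attached.

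Nor does the SAP state that a failed BuMA attempt counts against DP EES. That is the natural reading of an undefined term. The reversal in the illustration depends on its inputs: if the whole BuMA excess lies in crossovers and none occurs in the other direction, the sign changes at any crossover rate. Protocol 6.5 and 7.3.4 also call for the assigned stent at every target lesion and the same device for bailout, which should limit switching. Implanting a study stent before enrolment is a major deviation (Protocol 6.7), so non-randomised recipients may be few.

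All of this narrows the point. What remains is that the ITT-analysed events do not cover a procedural AE that neither leads to one of them nor is recorded as associated with a device deficiency. SAP 2.2.2.2 itself lists the switches that AT leaves unclassified. And although the protocol's ITT and PP tables are not expressly withdrawn, an analyst following the SAP table list would not produce them.

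**Conclusion.** The point holds in limited form. For the general AE, SAE and UADE summaries, the SAP departs from Protocol 11.4.7 in population and in MedDRA detail, and its AT set has no rule for failed, mixed or absent stents. Followed as written, it gives no comparison of general AEs by assigned arm, and procedural AEs outside the ITT-analysed events can be placed in the wrong column.

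The size cannot be determined from the documents. Starting from an assumed +1.0 point, moving 5 to 11 BuMA subjects (0.5% to 1.0% of 1088), all with the AE, gives −0.3 to −1.9 points. Milder inputs only dilute the difference, and the shift is about zero if crossovers have ordinary AE risk. The claim is that misattribution is possible and would go unseen in the general AE table, not that it will reverse the safety result. The primary endpoint is unaffected.

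**What to change.** 1. **SAP 5.6.1 and table list.** Restore the AE and SAE tables in ITT and PP, by MedDRA system organ class and preferred term, as Protocol 11.4.7 specifies. Keep Table 30 in AT as supportive.
2. **SAP 3.4.** Classify AT subjects by the first study device attempted at a target lesion, and by randomised arm if none was attempted. This settles the failed, mixed and no-stent cases and uses the attempt concept already in SAP 2.2.2.2 and 3.2.
3. **Non-randomised recipients.** Leave them out of the between-arm AT comparison and list them, with their AEs, separately.

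The cost is SAP wording and one repeated set of tables. Device attempts are already needed for the device-success analysis, whose categories also depend on whether the other device came after a failed or a successful use of the assigned one, so no new data should be required.

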## 4.0 GENERAL METHODOLOGY AND CONVENTIONS

Statistical analyses will be performed by the Cardiovascular Research Foundation using SAS® Software version 9.4 or higher. An independent programmer will validate all derived variables and analyses as defined in this SAP.

The primary safety and efficacy endpoint analysis will be performed after all eligible subjects have completed the 12 month follow-up assessment or reached the end of the assessment window. The secondary long-term safety and efficacy endpoint analysis will be performed after all patients have completed the 5 year follow-up assessment.

